5.4.1.9 Visit 10 (Week 14)

At Week 14, subjects will be classified as responders or nonresponders as per the definitions detailed in Section 5.2. This will be entered into the IWRS as described in a separate IWRS Manual. Subjects who are classified as nonresponders are prescribed 1 or both of 2 commercially available DMARDs as rescue medication in addition to the study treatment (see Section 6.13.3).

The following assessments will also be conducted at Visit 10:

- Perform joint counts (Independent Joint Assessment).
- Record AEs and injection site reactions that have occurred since the previous visit.
- Record details of contraceptive history/status.
- Record concomitant medications and concomitant non-drug therapies.
- Administer TB risk questionnaire.
- Perform partial physical examination (see Section 7.6.7.1).
- Record vital signs.
- Collect PK sample (see Table 5).
- Allocate study treatment through IWRS.
- Prescribe rescue medication for nonresponders.
- Administer study treatment.
 - If desired, SC injections may be rotated among the thighs and abdomen.

- All subjects will remain at the study site for 30 minutes after the injection to be assessed for onset of any systemic injection reactions.

5.4.1.10 Visit 11 (Week 16)

The following assessments will be conducted at Visit 11:

- Record AEs and injection site reactions that have occurred since the previous visit.
- Record details of contraceptive history/status.
- Record concomitant medications and significant concomitant non-drug therapies.
- Perform partial physical examination (see Section 7.6.7.1).
- Record vital signs.
- Collect samples for chemistry panel and hematology assessments.
 - Subjects must attend study sites after fasting (water and concomitant medications are permitted) for at least 9 hours for the purpose of conducting the chemistry panel.
- Collect PK sample (see Table 5).
- Perform urine pregnancy test for females of childbearing potential only.
- Allocate study treatment through IWRS.
- Administer study treatment.
 - If desired, SC injections may be rotated among the thighs and abdomen.
 - All subjects will remain at the study site for 30 minutes after the injection to be assessed for onset of any systemic injection reactions.

5.4.1.11 Visit 12 (Week 18)

The following assessments will be conducted at Visit 12:

- Administer Patient Global Assessment of Disease Activity (VAS).
- Administer Patient Assessment of Pain (VAS).
- Administer HAQ-DI.
- Perform joint counts (Independent Joint Assessment).
- Record AEs and injection site reactions that have occurred since the previous visit.

- Administer Physician Global Assessment (VAS).
- Record details of contraceptive history/status.
- Record concomitant medications and concomitant non-drug therapies.
- Record weight.
- Perform partial physical examination (see Section 7.6.7.1).
- Record vital signs.
- Collect sample to measure CRP level.
- Allocate study treatment through IWRS.
- Administer study treatment.
 - If desired, SC injections may be rotated among the thighs and abdomen.
 - All subjects will remain at the study site for 30 minutes after the injection to be assessed for onset of any systemic injection reactions.

5.4.1.12 Visit 13 (Week 20)

For subjects in the sample-rich PK subpopulation, Visit 13 (Week 20) should be scheduled to fall within 14 ± 2 days after Visit 12 (Week 18) and 28 ± 3 days after Visit 11 (Week 16).

The following assessments will be conducted at Visit 13:

- Record AEs and injection site reactions that have occurred since the previous visit.
- Record details of contraceptive history/status.
- Record concomitant medications and concomitant non-drug therapies.
- Perform partial physical examination (see Section 7.6.7.1).
- Record vital signs.
- Collect samples for chemistry panel and hematology assessments.
 - Subjects must attend study sites after fasting (water and concomitant medications are permitted) for at least 9 hours for the purpose of conducting the chemistry panel.
- Collect sample for analysis of ADAs.

- Collect PK sample (see Table 5).
 - Subjects in the sample-rich PK subpopulation will return to the study site for the collection of additional blood samples approximately 24 ± 8 hours (1 day ± 8 hours), 96 ± 24 hours (4 + 1 days), 168 ± 24 hours (7 ± 1 days), and 264 ± 24 hours (11 ± 1 days) following Visit 13.
- Perform urine pregnancy test for females of childbearing potential only.
- Allocate study treatment through IWRS.
- Administer study treatment.
 - If desired, SC injections may be rotated among the thighs and abdomen.
 - Subjects in the sample-rich PK subpopulation should use the same SC injection site (either abdomen or thigh) to administer the study treatment at Visit 2 and Visit 13 unless otherwise medically indicated.
 - All subjects will remain at the study site for 30 minutes after the injection to be assessed for onset of any systemic injection reactions.

5.4.1.13 Visit 14 (Week 22)

For subjects in the sample-rich PK subpopulation, Visit 14 (Week 22) should be scheduled to fall within 14 ± 1 days relative to study treatment administration at Visit 13 (Week 20).

The following assessments will be conducted at Visit 14:

- Record AEs and injection site reactions that have occurred since the previous visit.
- Record details of contraceptive history/status.
- Record concomitant medications and concomitant non-drug therapies.
- Perform partial physical examination (see Section 7.6.7.1).
- Record vital signs.
- Perform IGRA. If results are indeterminate, the IGRA can be repeated once.
- Collect PK sample (see Table 5).
 - For subjects included in the sample-rich PK subpopulation, the PK sample at Visit 14 (Week 22) should be collected prior to study treatment administration (336 ± 24 hours [14 ± 1 days] relative to Visit 13).

- Subjects in the sample-rich PK subpopulation will return to the study site for collection of an additional blood sample approximately 7 ± 1 days following Visit 14 (504 ± 24 hours [21 ± 1 days] relative to Visit 13).
- Allocate study treatment through IWRS.
- Administer study treatment.
 - If desired, SC injections may be rotated among the thighs and abdomen.
 - All subjects will remain at the study site for 30 minutes after the injection to be assessed for onset of any systemic injection reactions.

5.4.2 Visit 15/End of Treatment (2 Weeks after the Last Dose of the Study Treatment)/(Week 24)

The EoT Visit (Visit 15) will be performed 2 weeks after the last dose of study treatment for subjects who choose not to enter the OLE (Week 24) and for subjects who discontinue study treatment prematurely.

For subjects in the sample-rich PK subpopulation, Visit 15/EoT (Week 24) should be scheduled to fall within 28 ± 1 days relative to study treatment administration at Visit 13 (Week 20)

The following assessments will be performed at the EoT Visit for all subjects:

- Administer Patient Global Assessment of Disease Activity (VAS).
- Administer Patient Assessment of Pain (VAS).
- Administer HAQ-DI.
- Administer SF-36, EQ-5D, FACIT-Fatigue, and WPS-RA.
- Perform joint counts (Independent Joint Assessment).
- Record AEs and injection site reactions that have occurred since the previous visit.
- Administer Physician Global Assessment (VAS).
- Record details of contraceptive history/status.
- Record concomitant medications and concomitant non-drug therapies.
- Administer TB risk questionnaire.
- Record weight.

- Perform complete physical examination (see Section 7.6.7.1).
- Record vital signs.
- Perform chest X-ray.
 - Chest X-ray need not be conducted if performed and evaluated within 8 weeks prior to the EoT Visit, and if the films or images are available and included in the subject's source documents.
- Perform 12-lead ECG.
- Collect samples for INR, aPTT, and fibrinogen.
- Measure ESR.
- Collect sample to measure CRP level.
- Collect samples for lipid panel and CV risk panel.
 - Subjects must attend study sites after fasting (water and concomitant medications are permitted) for at least 9 hours for the purpose of conducting the lipid panel assessment.
- Collect sample for serum biomarkers related to targeted pathway.
- Collect samples for chemistry panel, hematology, ANAs, and dsDNA antibodies assessments.
 - Subjects must attend study sites after fasting (water and concomitant medications are permitted) for at least 9 hours for the purpose of conducting the chemistry panel.
- Collect samples for measurement of anti-CCP and RF.
- Collect PK sample (see Table 5).
- Collect sample for analysis of ADAs.
- Perform urine pregnancy test for females of childbearing potential only.
- Collect sample for urinalysis.

5.4.3 Safety Follow-up: Visits SFU-1, SFU-2, and SFU-3

5.4.3.1 Visit SFU-1 (Week 26 or 4 Weeks after the Last Dose of the Study Treatment)

The following assessments will be conducted 4 weeks after the last dose of the study treatment:

- Record AEs.
- Record details of contraceptive history/status.
- Record concomitant medications and concomitant non-drug therapies.
- Record weight.
- Perform partial physical examination (see Section 7.6.7.1).
- Record vital signs.
- Collect sample to measure CRP level.
- Perform urine pregnancy test for females of childbearing potential only.

5.4.3.2 Visit SFU-2 (Week 30 or 8 Weeks after the Last Dose of the Study Treatment)

The following assessments will be conducted 8 weeks after the last dose of the study treatment:

- Record AEs.
- Record details of contraceptive history/status.
- Record concomitant medications and concomitant non-drug therapies.
- Administer TB risk questionnaire.
- Record weight.
- Perform partial physical examination (see Section 7.6.7.1).
- Record vital signs.
- Collect sample to measure CRP level.
- Collect samples for chemistry panel and hematology assessments.
 - Subjects must attend study sites after fasting (water and concomitant medications are permitted) for at least 9 hours for the purpose of conducting the chemistry panel.

- Collect PK sample (see Table 5).
- Collect sample for analysis of ADAs.
- Perform urine pregnancy test for females of childbearing potential only.

5.4.3.3 Visit SFU-3 (Week 44 or 22 Weeks after the Last Dose of the Study Treatment)

The following assessments will be conducted 22 weeks after the last dose of the study treatment:

- Record AEs.
- Record details of contraceptive history/status.
- Record concomitant medications and concomitant non-drug therapies.
- Record weight.
- Perform complete physical examination (see Section 7.6.7.1).
- Record vital signs.
- Perform 12-lead ECG.
- Collect samples for INR, aPTT, and fibrinogen.
- Collect samples for lipid panel and CV risk panel.
 - Subjects must attend study sites after fasting (water and concomitant medications are permitted) for at least 9 hours for the purpose of conducting the lipid panel assessment.
- Collect samples for chemistry panel, hematology, ANAs, and dsDNA antibodies assessments.
 - Subjects must attend study sites after fasting (water and concomitant medications are permitted) for at least 9 hours for the purpose of conducting the chemistry panel.
- Collect sample for analysis of ADAs.
- Perform urine pregnancy test for females of childbearing potential only.
- Collect sample for urinalysis.

5.4.4 Screen Failure and Re-Screening

Subjects who are considered to be screen failures must be recorded as such in the IWRS.

At a minimum, the demographics and eligibility criteria (i.e., inclusion and/or exclusion criteria) are to be documented in the eCRF for all screen failures.

Subjects who are screen failures may be re-screened with prior approval of R-Pharm or R-Pharm's designee. The IWRS will assign a new subject number and all Screening assessments must be repeated (see Section 5.4.1.1), with the following exceptions:

- Chest X-ray does not need to be repeated if a chest X-ray was performed within 8 weeks prior to the date of re-screening and films or images are available for review.
- For subjects with documented LTBI who have completed at least 30 days of TB prophylaxis, the IGRA does not need to be repeated at the re-screening visit.

5.4.5 **Unscheduled Visit**

It is at the Investigator's discretion to initiate an Unscheduled Visit, if deemed necessary by the Investigator for the subject's safety and well-being. At this visit, any of the assessments from the Schedule of Events may be performed dependent on the presenting reason. When a protocol-required procedure cannot be performed at the scheduled time the Investigator will document in the source documents the reason for this and any corrective and preventive actions that he/she has taken to ensure that normal processes are adhered to as soon as possible. R-Pharm's designee should be informed of these incidents in a timely fashion.

6. STUDY TREATMENTS

6.1 Study Treatment Administered

Study Treatment

All eligible subjects will be randomly assigned in a 1:1:1 ratio to the OKZ and placebo treatment groups described in Section 5.2. A detailed description of the study treatment (OKZ and placebo) is provided in Section 6.2.

Background Therapy

All subjects will continue to receive their prior background therapy (MTX) during the study.

As per inclusion criterion No. 4 (see Section 5.3.1), subjects must have been treated with MTX at a dose of 15 to 25 mg/week (or ≥ 10 mg/week if there is documented intolerance to higher doses) for at least 12 weeks prior to Screening with a stable dose and an unchanged mode of administration (oral, SC, or IM) for at least 6 weeks prior to Screening.

The dose of background MTX should remain unchanged throughout the study and may be adjusted only for safety reasons according to Investigator discretion. If the Investigator judges that the dose of MTX must be adjusted for safety reasons, this may only be done once during the study. If needed, a reduction in the MTX dose may be made according to the guidelines in Appendix 4 (see Section 13.4).

Rescue Medication

Starting at Week 14, nonresponders will be assigned rescue medication (sulfasalazine and/or hydroxychloroquine) in addition to their assigned study treatment (see Section 6.13.3).

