5.2 Discussion of Study Design

Once subjects have successfully completed the 4-week Screening Period, a total of 420 subjects will be randomized in a 1:1:1 ratio (140 subjects per treatment group) to 1 of 3 treatment groups as follows:

1. OKZ 64 mg q4w: SC injection of OKZ 64 mg q4w (alternating with SC injection of placebo OKZ q4w to maintain blinding) + MTX.
2. OKZ 64 mg q2w: SC injection of OKZ 64 mg q2w + MTX.
3. Placebo: SC injection of placebo q2w + MTX.

This is a double-blind study; as the placebo differs in appearance from OKZ, study treatment will be prepared by an independent unblinded pharmacist or designee (e.g., nurse) and provided to blinded site staff in blinded syringes that are identical in appearance. The SC injections of OKZ and placebo will be administered every other week by blinded trained study staff. As noted above for treatment group No. 1, in order to maintain the blind, subjects randomized to receive OKZ q4w will receive placebo injections at the alternate q4w interval (e.g., Week 2, Week 6, etc.) at prespecified visits as described in Table 1 or Table 2 (as applicable).

Throughout the double-blind Treatment Period, all subjects will be required to remain on a stable dose of background MTX at 15 to 25 mg/week (or ≥ 10 mg/week if there is documented intolerance to higher doses) with a stable route of administration, and concomitant treatment with folic acid ≥ 5 mg per week or equivalent is required for all subjects. From Week 0 through Week 24, subjects will return to the study site at least every other week for response and safety assessments as per Table 1 or Table 2 (as applicable). Blood samples to assess OKZ concentrations in plasma will be collected periodically during the Treatment Period as per Table 5.

Subjects will be classified in terms of their response to study treatment at Week 14, with nonresponders defined as subjects from any treatment group who do not improve by at least 20% in both SJC and TJC (66-68 joint assessment). Starting at or as close as possible to Week 14, nonresponders in all groups will be administered sulfasalazine and/or hydroxychloroquine as rescue medication in addition to their assigned treatment (see Section 6.13.3).

The last dose of study treatment (OKZ or placebo) will take place at Week 22.

After completion of the 24-week double-blind Treatment Period, subjects will be offered the opportunity to enter the long-term OLE study. Subjects who do not consent to participate in

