6.13 Prior and Concomitant Treatments

Concomitant treatment with MTX is detailed in Section 6.1. Specifically, at the discretion of the Investigator, the dose of MTX can be reduced once during the study for safety reasons according to the guidelines in Appendix 4 (see Section 13.4).

Concomitant treatment with folic acid ≥ 5 mg per week or equivalent is required for all subjects starting by Visit 2 (Week 0). Folic acid or equivalent should not be taken on the same day as MTX.

Other specifically allowed medications are discussed in Section 6.13.2.

Specific treatments prohibited prior to (as applicable) and during the course of the study are described in Table 4. Other medications and non-drug therapies not listed within Table 4 that are considered necessary for the subject's safety and well-being may be given at the discretion of the Investigator and recorded in the appropriate sections of the eCRF. All medications/treatments received within 4 weeks prior to the Screening Visit will be recorded in the eCRF. Prior MTX and all other treatments for RA for the 6 months prior to the Screening Visit will be recorded in the eCRF. Doses, route of applications, duration of treatment, and reasons for prescription are also to be recorded.

A caution regarding cytochrome P (CYP) and transporter proteins is discussed in Section 6.13.1.

Table 4 Prohibited Medications

Treatment	Restriction

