13.4 Appendix 4: Methotrexate Dose Reduction Guidelines

ALT and/or AST	Total Bilirubin	Repeat Laboratory	MTX	Study Treatment
1× to ≤2× ULN	<2× ULN	No need	No change	No change
>2× to ≤3× ULN	<2× ULN	Within 1 week	No change or can consider reduction in dose	No change
If repeat >2× to ≤3× ULN	<2× ULN	Within 1 week	Reduce dosage and follow LFTs	No change
>3× to ≤8× ULN (without the appearance of fatigue, nausea, vomiting, right upper quadrant pain or tenderness, fever, or rash)	≤2× ULN	Within 72 hours of initial finding, and then at least weekly after last finding until resolution, stabilization, or return to baseline values	Hold MTX until LFTs normalize or return to baseline and consider restarting at lower dose	No change
If repeat >3× to ≤8× ULN (without the appearance of fatigue, nausea, vomiting, right upper quadrant pain or tenderness, fever, or rash)	≤2× ULN	Within 72 hours of initial finding, and then at least weekly after last finding until resolution, stabilization, or return to baseline values	Hold MTX until LFTs normalize or return to baseline and consider restarting at lower dose	Hold and consider restarting after discussion with the R-Pharm Medical Advisor or designee
>3× ULN with appearance of fatigue, nausea, vomiting, right upper quadrant pain or tenderness, fever, rash, and/or eosinophilia (>5%)	≤2× ULN	Within 72 hours of initial finding, and then at least weekly after last finding until resolution, stabilization, or return to baseline values	Hold MTX. Follow local Standard of Care.	Permanently discontinue study treatment
>3× ULN	>2× ULN	Within 72 hours of initial finding, and then at least weekly after last finding until resolution, stabilization, or return to baseline values	Hold MTX. Follow local Standard of Care.	Permanently discontinue study treatment
>5× ULN for more than 2 weeks	≤2× ULN	Within 72 hours of initial finding, and then at least weekly after last finding until resolution, stabilization, or return to baseline values	Hold MTX. Follow local Standard of Care.	Permanently discontinue study treatment

R-Pharm
 CL04041022: Clinical Rheumatoid Arthritis Development for Olokizumab (CREDO) 1
 Olokizumab

ALT and/or AST	Total Bilirubin	Repeat Laboratory	MTX	Study Treatment
>8× ULN	≤2× ULN	Within 72 hours of initial finding, and then at least weekly after last finding until resolution, stabilization, or return to baseline values	Hold MTX. Follow local Standard of Care.	Permanently discontinue study treatment

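### Sections 6.1 and 6.13 cap methotrexate at one safety change per study, but Appendix 4 directs more than one step on some liver-enzyme paths and mentions no cap

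*Combined protocol and SAP*

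**What the plan says.** Section 6.1 (Background Therapy) keeps the MTX dose fixed apart from safety changes, which are left to the investigator. If the dose "must be adjusted for safety reasons, this may only be done once during the study". It then brings in the table: "If needed, a reduction in the MTX dose may be made according to the guidelines in Appendix 4".

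Section 6.13 gives the same limit in a different term: "the dose of MTX can be reduced once during the study for safety reasons according to the guidelines in Appendix 4".

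Section 6.10 also sends the reader to Appendix 4 for MTX reductions and states no limit.

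Appendix 4 is a table of ALT/AST bands. Three of its MTX instructions matter here:

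- Row A, first result above 2 and up to 3 times ULN: "No change or can consider reduction in dose".
- Row B, repeat result still in that band: "Reduce dosage and follow LFTs".
- Row C, above 3 and up to 8 times ULN without the listed symptoms, with the same MTX text for the initial and the repeat result: "Hold MTX until LFTs normalize or return to baseline and consider restarting at lower dose".

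Appendix 4 does not refer back to the limit of one.

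**The concern.** The cap runs for the whole study, while the table responds to each laboratory result. A subject whose enzymes stay raised or rise again can reach a second MTX instruction after the single permitted change has been used. The site must then either follow the table and breach Section 6.1, or keep to Section 6.1 and leave a directed safety step undone.

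The wording does not settle the matter. Section 6.1 speaks of an *adjustment* and Section 6.13 of a *reduction*. Neither says whether a hold, or a hold followed by a restart, is the one permitted change. Sites could reasonably read this differently and so handle background therapy differently.

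**Working it through.** The plan has no figure to reproduce here. The check is to count MTX changes along each path through Appendix 4 and compare the count with the limit of 1.

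**Inputs.** The limit of 1 comes from Sections 6.1 and 6.13, and rows A, B and C from Appendix 4. The four rows that also stop study treatment permanently direct a hold too, but they pass MTX to local standard of care and are left out of the count.

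**Changes contributed by each row:**

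- Row A: 0 or 1, because the reduction is optional.
- Row B: 1, because the reduction is directed.
- Row C: the hold is directed and the lower-dose restart is only to be considered. The contribution is 0 or 1 if only dose reductions count, 1 if a hold with its restart counts as one adjustment, and 1 or 2 if the hold and a lower-dose restart count separately.

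**Minimum to maximum changes per path:**

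| Path | Reductions only | Hold episode = one | Hold and lower restart separate |
|---|---|---|---|
| A, then B | 1–2 | 1–2 | 1–2 |
| C alone | 0–1 | 1 | 1–2 |
| A, then C | 0–2 | 1–2 | 1–3 |
| A, B, then C | 1–3 | 2–3 | 2–4 |
| A, B, then B again | 2–3 | 2–3 | 2–3 |

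For the fourth path:

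- Reductions only: 0+1+0 = 1 to 1+1+1 = 3.
- Hold episode as one: 0+1+1 = 2 to 1+1+1 = 3.
- Counted separately: 0+1+1 = 2 to 1+1+2 = 4.

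**Reading the table:**

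- The first three paths can all meet the limit of 1. No change followed by one reduction does so, and so does a single hold episode counted as one adjustment.
- Path A, B, C meets the limit only if a hold is not an adjustment and no lower-dose restart follows. Otherwise it is over the limit on directed steps alone, with no change made at row A.
- Path A, B, B is over the limit under every reading. It assumes that row B applies again to a further result in the band, which Appendix 4 does not expressly say.

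**The case against.** The strongest reply is that Appendix 4 is invoked permissively, as guidelines for a change made at the investigator's discretion, and that the cap governs how that discretion is used. The row A reduction and the lower-dose restart are both optional. A hold is arguably not a reduction, which is the term Section 6.13 uses.

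Much of this stands. A reader might infer that no subject with persistent ALT/AST elevation can be managed within both rules. The documents do not support that: the table prescribes only one reduction outright, and the first three paths above can comply.

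The reply does not remove the conflict. Rows B and C direct a reduction and a hold without relying on any optional step. Treating a hold as outside the cap rests on Section 6.13's narrower term, whereas Section 6.1's word is broader. If a hold is not an adjustment, Section 6.1, which mentions only adjustment and reduction, does not address holds at all.

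A reader might also infer that the stable-dose rule lacks a safety exception, since Section 5.2 says that "all subjects will be required to remain on a stable dose of background MTX at 15 to 25 mg/week". That is not a fault. Section 6.1 states the exception, and Sections 6.10 and 6.13 repeat the route to Appendix 4.

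**Conclusion.** Wrong as written: an internal contradiction in a safety rule, confined to some paths. It should be corrected. The size is at least 2 changes against a limit of 1 when row B is followed by row C and a hold counts, and at least 2 under every reading if row B is met again. The first result rests on how a hold is classed, the second on row B applying more than once. The documents settle neither.

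Three further inferences are tempting but unsupported:

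- **A heavier burden on the olokizumab arms.** The Study RA0056 summary in Section 2.2.3.2 lists ALT increased, AST increased and abnormal liver function test among events in at least 10% of subjects in any olokizumab group. It gives no placebo rate for these terms and no ULN multiple. The group percentages imply 20 to 23 subjects per group (14 is 70.0% of 20; 20 is 87.0% of 23), so 10% can be 2 or 3 people.
- **Loss of subjects from the Per Protocol population.** No section classes an MTX change as a major violation. Section 9.3 leaves those violations to be defined before unblinding, and the Per Protocol analysis is only supportive.
- **A count of affected subjects per arm.** The rate of ALT/AST above 2 times ULN is not given, nor the share of subjects who would need a second step, so any count would be guesswork.

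**What to change.** Reconcile Section 6.1, Section 6.13 and Appendix 4:

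- Use one term in all three places, and state in Appendix 4 whatever limit applies.
- Say whether the limit covers reductions, holds and restarts, and whether a hold followed by a restart counts as one change.
- Say whether the repeat row applies again to a further result in the same band.
- Say what applies once the limit has been reached.

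Which clinical rule applies, including the number of changes allowed, is for the sponsor's medical team. The cost is wording in three places in an amendment, with no new procedures, visits or data.
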